#### **A. Reporting requirements when a procedure is suspended**

A protocol deviation or violation, informed consent violation, or adverse event that results in suspension of a procedure must be reported within three working days to the DCC, Steering Committee, NHLBI, and the DSMB.

#### **B. Reporting requirements for Adverse Events**

The adverse event form must be completed for all AEs as defined above for SARP III. Forms on which procedure results are recorded contain an area to indicate the occurrence of additional treatment required during or immediately after the procedure. If this area is marked, a subsequent Additional Treatment form will be filled out and sent to the DCC with information from the procedure. During the course of their evaluation, subjects will be asked about the occurrence of AE-like events and this also will be reported to the DCC. Subjects will be monitored after their last visit specified by this protocol for a period of time consistent with observing any AEs that might have occurred due to protocol procedures. Any that occur will be reported to the DCC. Any AE-like events that are observed in a subject's medical record during the period that they are enrolled in SARP will be reported.

The supplemental SAE form must be completed for all SAEs: the lone exception is unanticipated non-fatal SAEs that are not possibly related to the protocol. For unanticipated non-fatal SAEs that are unrelated to the protocol, the Principal Investigator has discretion about reporting to the DCC. The Principal Investigator will report all anticipated SAEs and all unanticipated SAEs that are possibly, probably, or definitely study-related to the DCC and the local IRB within 3 business days of the time that the Investigator learns of the event; any fatality will be reported within 24 hours. Local IRBs may have different requirements for reporting unrelated SAEs and the Principal Investigator must adhere to local requirements in addition to SARP requirements. The DCC will then forward all SAE reports to the DSMB and NHLBI within 48 hours of receipt from the clinical center. Asthma exacerbations and other asthma-related SAEs that occur more than 30 days after the most recent study visits will not follow this expedited reporting, but will be reported in summary fashion at each DSMB meeting.

The DCC will prepare a monthly report for the Steering Committee on all AEs, SAEs and monitored data. The Steering Committee will have current information about the occurrence of these events in the study as a whole and in each of the clinical centers. The Steering Committee is empowered to take corrective action if these reports indicate the development of any undue risk for subjects. In addition a similar report will be prepared for the DSMB at its bi-monthly meetings.

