**Withholding medication:** After consenting, subjects will be asked to hold certain medications prior to each visit for the purpose of lung function testing. Subjects may experience an increase in their asthma symptoms from holding their daily medications. If subjects are unable to hold their medications, they are instructed to take the medication as needed and to call the study staff. This will also be documented and the subject will proceed with the scheduled procedure.

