## **VI. DATA AND SAFETY MONITORING BOARD**

A DSMB was established by the NHLBI in accordance with NIH policies and is responsible for monitoring of patient safety and review of study performance. The DSMB consists of a chair, clinicians with expertise in asthma management, scientists with expertise in asthma

clinical research, bioethics, and biostatistics. An NHLBI scientist other than the NHLBI's SARP Project Scientist serves as the Executive Secretary to the DSMB. The DSMB meets approximately bi-monthly by teleconference or in-person meetings in Bethesda, MD. The DSMB reviews serious adverse event reports on an ongoing basis, according to NHLBI policies. Following each meeting, the DSMB submits recommendations to NHLBI regarding the continuation of clinical research projects. The NHLBI addresses the recommendations and prepares a report for principal investigators that can be provided to their institutional review boards.

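### The 30-day rule ends expedited reporting of asthma SAEs on elapsed time alone, so one that starts during the medication hold before an unsplit V4-V9 goes to summary reporting even if judged study-related

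*Combined protocol and SAP*

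**What the plan says.** Section V.B first sets a general rule: "The Principal Investigator will report all anticipated SAEs and all unanticipated SAEs that are possibly, probably, or definitely study-related to the DCC". The IRB is told as well; the deadline is 3 business days, or 24 hours for a death. A forwarding step comes next: "The DCC will then forward all SAE reports to the DSMB and NHLBI within 48 hours of receipt from the clinical center".

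The last sentence of the same paragraph makes an exception: "Asthma exacerbations and other asthma-related SAEs that occur more than 30 days after the most recent study visits will not follow this expedited reporting". Those events are instead summarised for the board whenever it meets. On meeting frequency, Section VI says: "The DSMB meets approximately bi-monthly by teleconference or in-person meetings".

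Section IV.B, which lists the adverse events expected from taking part, has a paragraph on withholding medication. Once consent is given, "subjects will be asked to hold certain medications prior to each visit for the purpose of lung function testing". The paragraph names the risk of doing so: "Subjects may experience an increase in their asthma symptoms from holding their daily medications". Those who cannot hold are told to take the medication as needed and call the staff. Section III.E leaves the details of withholding to the MOPs.

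**The concern.** An elapsed-time rule can stand in for a judgement that the study did not cause an event only if the study's risks follow its visits. The medication hold is a risk that comes before a visit. While a hold is under way, the visit it prepares for has not taken place, so the 30-day clock still runs from the previous one. An asthma SAE starting in that interval can be a direct consequence of a protocol procedure and yet be handled as background disease.

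At stake is how soon the DSMB learns of it. The hold recurs before each visit, in a cohort that includes subjects with severe asthma. If it caused serious exacerbations, the board would need to hear of them individually and soon, as it does for other study-related SAEs.

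**Working it through.** The 30 days is a reporting rule, not a derived figure, so there is nothing to reproduce. The check is date arithmetic on the visit windows.

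**Inputs**
- V3: 18 ± 3 days after V2 (Section III.D, Appendix 1).
- V4, V5, V6: 12, 24 and 36 months from enrollment, ± 90 days. V7: 48 months ± 90 days. V8 and V9: annual ± 90 days (Section III.D, Appendix 1).
- Telephone contacts: every 12 months from month 6, ± 60 days (Section III.D).
- Assumption: hold length 0.25 to 7 days. The protocol gives none.
- Assumption: V2 up to 42 days after V1, with V1 as enrollment. Appendix 1 asks only for maximal bronchodilation within 6 weeks of V2, so this is not a stated limit.
- One month = 365.25/12 days.

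**Formula.** Minimum gap = nominal interval − late window of the earlier contact − early window of the later visit.

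**Clinic visit to clinic visit**
- V4 to V5, and each later pair through V9: 365.25 − 90 − 90 = 185.25 days. If the V8 and V9 windows run from the previous visit rather than from enrollment, the gap is longer: 365.25 − 90 = 275.25 days.
- V3 to V4: 365.25 − 90 − (42 + 21) = 212.25 days. With V1 and V2 on the same day: 365.25 − 90 − 21 = 254.25 days. To bring the gap down to 30 days, V2 would have to be 365.25 − 90 − 21 − 30 = 224.25 days after V1.
- Earliest onset during a 7-day hold: 185.25 − 7 = 178.25 days after the previous clinic visit, far beyond day 30.

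**V2 to V3.** 15 to 21 days, inside the 30 days. The problem starts at V4.

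**If telephone contacts count as study visits**
- Minimum gap from call to next visit: 182.625 − 60 − 90 = 32.6 days (31 to 34 days by calendar date).
- Less a hold of 1, 2, 3 or 7 days: 31.6, 30.6, 29.6 or 25.6 days. At the window extremes, a hold of about 3 days or more would fall within the 30 days.
- This margin also assumes that V8 and V9 are timed from enrollment. Appendix 1 states that anchor only through V6.

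**The rules side by side.** Suppose an asthma SAE starts during the hold before an unsplit V5.
- General rule: if the event is classed as anticipated, it is expedited. If it is classed as unanticipated, it is expedited when at least possibly study-related.
- Exception: it occurs more than 30 days after V4, so it goes to the summary whatever its class or cause.

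**Delay to the DSMB.** The general rule gives 3 business days (3 to 5 calendar days, ignoring holidays) plus 2 days, so 5 to 7 days. The exception gives up to one meeting interval: about 365.25/24 = 15 days if the board meets twice a month, or 365.25/6 = 61 days if every two months.

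**The case against.** A reader might infer that every SAE caused by a hold escapes expedited reporting. The documents do not support that. Onset at or after the visit is day 0 or later from that visit. V4 and V5 may be split in two, and the V6 fasting draw may fall on another day, so the first part can become the latest visit. Appendix 2 adds ancillary and exacerbation visits. The protocol does not say which of these, or whether telephone contacts, count as study visits. These points stand, and they limit the finding to onset during the hold before an unsplit visit with no recent extra visit.

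Nor do the documents say that controller drugs in particular are held, or that every subject holds. They speak of certain medications and let subjects who cannot hold take them. The named risk is more symptoms; a hospitalised exacerbation is a plausible extension, and no frequency is given.

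The exemption may also be narrower than it looks. It directly follows the DCC's 48-hour step, so it could be read as replacing that step alone, leaving the 3-business-day report and the 24-hour report of deaths in force. The text does not settle this. On either reading, prompt notice to the DSMB is lost.

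Other routes exist. The Steering Committee receives a monthly report and can act on it (Section V.B). The investigator must keep the IRB informed of SAEs (Section V.F). An event that suspends a procedure reaches the DSMB within three working days (Section V.A). None of these gives the DSMB prompt notice of a hold-related SAE that does not suspend a procedure.

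Finally, keeping background exacerbations out of expedited reporting is a sensible choice in this cohort. Nothing suggests, however, that it was meant to cover events judged study-related.

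**Conclusion.** The concern holds in limited form. By elapsed time alone, Section V.B moves an asthma SAE that starts during the hold before an unsplit V4-V9 to summary reporting, even if judged study-related, against its own general rule. The result is not close when scheduled clinic visits are counted: at least about 178 days against a cut-off of 30, for holds of up to 7 days. For V4 it also assumes that V2 is within 42 days of V1, but only a gap of about 224 days would reverse it. It is close only if telephone contacts count as study visits (about 33 days before subtracting the hold).

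The added delay to the DSMB ranges from roughly one week to nearly two months, depending on the meaning of the meeting interval. The number of events cannot be estimated from the documents. A reader might also infer that these events go unreported, or that the DSMB could not tell them from background exacerbations. The first is wrong, since they reach the DSMB in summary and the Steering Committee monthly. The second cannot be judged, because neither the SAE form nor the summary layout is shown. No efficacy or cohort analysis is affected; this is a gap in safety oversight.

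**What to change.** In Section V.B:
- limit the 30-day exemption to asthma-related SAEs that the investigator judges not related to the protocol;
- state that it does not apply to an event that starts during a protocol-required medication hold;
- say which contacts count as a study visit (split, ancillary, exacerbation and telephone contacts);
- say which steps the exemption replaces: the 3-business-day report, the 48-hour forwarding, or both, and whether the 24-hour report of deaths still applies.

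The cost is a short edit to one section and a few more expedited reports. Background exacerbations stay in the summary. The change concerns reporting only and leaves the hold itself as it is.

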#### **C. Reporting genetic data**

As part of the genetic study, a sample of DNA may have Genome Wide Association Studies (GWAS) or Whole Genome Sequencing (WGS) performed. Information regarding the subject's DNA and clinical information will be sent to the National Institute for Health's Genome Wide

Association Study (GWAS) data repository, dbGaP, where it will undergo genome-wide analysis and be shared with other investigators for research purposes. Before the information is sent to the GWAS data repository it will be de-identified.

#### **D. Subject privacy and data collection**

The privacy of participating adult and pediatric subjects and their families will be protected in accordance with the Health Insurance Portability and Accountability Act (HIPAA) guidelines. After enrollment, for subject protection, the SARP DCC will assign a unique identifier to each subject. This unique identifier from this point on will identify all testing results, specimens and data entered into the central database. All data obtained will be numerically coded and only the Principal Investigator and his or her designees trained in human subjects' protection will be able to link a subject's identity with his or her name at the clinical centers. The list of identities and participant identification codes is maintained on a password-protected file on the research coordinator's computer, along with back-up files of research data obtained from that subject. Computers are maintained by Information Technology staff and monitored daily for security threats. The password-protected data files are backed up nightly for safekeeping. The primary data files for participating subjects are expected to be housed at the DCC using numerical identification codes. The DCC is not expected to have access to participants' names, addresses, or other identifying information, nor will it be stored in the study database at the DCC.

Procedures related to protected health information (PHI) collected for the purposes of this research will be disclosed to potential subjects and their parents or guardians during the process of informed consent/assent. A separate signature authorizing the collection of PHI will be obtained within the consent form. PHI may be disclosed to: 1) governmental agencies overseeing the project, such as the National Heart, Lung and Blood Institute of the National Institutes of Health to monitor safety, efficacy and compliance with laws and regulations; 2) university personnel charged with oversight of research, such as the Institutional Review Board, to monitor safety and compliance with applicable laws, regulations, and University policies and procedures; 3) statisticians at the DCC for the purposes of data analysis and interpretation; 4) the SARP Data Safety and Monitoring Board, and 5) researchers within the SARP network, to report serious adverse events and issues that might arise during the course of the study.

Procedures for all data collection are provided in the Manual of Procedures. Information is collected on pre-defined forms at the clinics and transmitted to the DCC over an encrypted internet connection. All data are collected for research purposes and this is noted in the informed consent. No data in pre-existing health records are used as part of this data collection.

#### **E. Sample collection, handling and storage**

Samples collected under this study will be collected, handled and stored as previously described in the SARP MOP. All procedures and sample handling are described in detail in the SARP MOP.

Briefly, samples will be collected (as outlined in the MOP) and labeled with only a SARP ID number, date of collection and sample type. The samples will be stored at each individual SARP

site unless specified for shipment and storage in the SARP MOP. The specimens will be used to answer questions related to the long-term health effects of subjects with severe asthma compared to subjects with milder asthma. The SARP Steering Committee will be responsible for distributing the samples to other research centers in SARP to help them answer their specific research questions pertaining to the long term health effects of severe asthma. If the subject does not consent to have his/her samples shared, they will remain at the specific center where they were collected.

When the samples are collected, they will be labeled with an ID number only, with the identifying data kept in a locked drawer or a password protected computer file. Access to this file will be available the PI at each participating site and the data coordinating center. This code number will be linked to the other common SARP procedure data i.e. demographics, questionnaire information. This information is available to all the SARP investigators but without subject name or social security number. The DCC is responsible for linking all the data from the common SARP procedures to the subject identification number.

The current planned analysis on the specimens collected will be to meet the objectives stated in the protocol. If new objectives or research questions are developed at a future time, a separate application will be filed with the IRB. Each subject will have the ability to opt out of having their samples stored for future unspecified use without having an effect on their participation in the current study. In summary, the samples are stored at the specific site where they were collected unless shipment and storage to another site is specified in the MOP. These samples will be used to answer site-specific research questions pertaining to the protocol objectives. Each site may use samples from other sites in SARP to help answer those questions.

## **F. Ethical considerations**

1. The procedures set out in this protocol, pertaining to the conduct, evaluation, and documentation of this study, are designed to ensure that the investigator abide by Good Clinical Practice Guidelines (GCP)(E6) and under the guiding principles detailed in the Declaration of Helsinki. The study will also be carried out in keeping with applicable local law(s) and regulation(s).

The investigator is responsible for complying with the protocol and all appropriate regulations and guidelines governing global clinical research. Additionally, he/she is responsible for ensuring that all participating staff members are adequately trained and competent to perform his/her assigned tasks.

2. This protocol, informed consent document, relevant supporting information, and all types of subject recruitment or advertisement information must be submitted to the IRB for review and must be approved by the IRB before the study is initiated. Any amendments or addenda to the protocol must also be approved by the IRB prior to implementing changes in the study. The Investigator is responsible for keeping the IRB apprised of the progress of the study and of any changes made to the protocol as deemed appropriate, but in any case at least once a year. The Investigator must also keep the IRB informed of any SAEs occurring to subjects under their supervision.

In addition as required by the NIH an independent DSMB, under NIH auspices, has been assembled to monitor this study.

3. Prior to the beginning of the study, the investigator must have the IRB written approval/favorable opinion of the written Informed Consent Form and any other written information to be provided to subjects. The written approval of the IRB together with the approved subject information/Informed Consent Forms must be filed in the study files. The Informed Consent Form must contain all elements required by the FDA under 21 CFR Part 50 and the ICH GCP Guidelines in addition to any other elements required by state, local or institutional policy

Written informed consent must be obtained before any study specific procedure takes place. Participation in the study and date of informed consent given by the subject should be documented appropriately in the subject's files. A copy of the signed informed consent form must be provided to the subject. If applicable, it will be provided in a certified translation in the language understood by the subject if not English. Signed consent forms must remain in each subject's study file and must be available for verification by study monitors at any time.

Each subject is required to sign a HIPAA Research Authorization at the time of consent. This authorization clearly outlines who will have access to specified protected health information. The data will be coded by subject identification numbers and any key linking this code number to subject identifiers will have access limited to the investigator and key study personnel all of whom have had HIPAA training. Data will be stored in files and a computer database, both in a locked location with access only by study personnel. Data obtained from the study may be published in scientific journals or presented in scientific meetings but results will be coded so individuals are not identified. The Principal Investigator will retain records for at least two years after the investigation is discontinued and the FDA is notified. This is in accordance with US FDA Regulation (21CFR 312.62 (c)).

4. Subjects will be recruited for this study using IRB approved print advertisements, public study-specific posters, IRB approved websites, television ads and use of a mass email students/faculty/etc.
5. The information obtained during the conduct of this study is confidential, and disclosure to third parties other than those noted below is prohibited. Subject-specific information may be provided to other appropriate medical personnel only with the subject's permission. To ensure compliance with current ICH guidelines, data generated by this study must be available for inspection upon request by representatives of national and local health authorities, and the IRB for each study site.

Subject names and other identifiers, such as photographs, audio or videotapes, may not be disclosed in any publication without prior written authorization from the subject.

## **VI. DATA AND SAFETY MONITORING BOARD**

A DSMB was established by the NHLBI in accordance with NIH policies and is responsible for monitoring of patient safety and review of study performance. The DSMB consists of a chair, clinicians with expertise in asthma management, scientists with expertise in asthma

clinical research, bioethics, and biostatistics. An NHLBI scientist other than the NHLBI's SARP Project Scientist serves as the Executive Secretary to the DSMB. The DSMB meets approximately bi-monthly by teleconference or in-person meetings in Bethesda, MD. The DSMB reviews serious adverse event reports on an ongoing basis, according to NHLBI policies. Following each meeting, the DSMB submits recommendations to NHLBI regarding the continuation of clinical research projects. The NHLBI addresses the recommendations and prepares a report for principal investigators that can be provided to their institutional review boards.

